2.1. Background and Rationale

Several studies have demonstrated that music can improve various outcomes during labor and delivery. However, many of these studies suffer from severe methodological flaws. In particular, patient satisfaction is often measured on a simple VAS scale, where 0 is no satisfaction and 10 is the highest satisfaction. However, patient satisfaction is a complex parameter to measure, and may be affected by a number of different factors. This will be the first study performed on the labor and delivery unit to assess patient satisfaction with a validated, reliable, 22-question survey developed by Morgan et al. (Morgan 1999), in the setting of music or no music during the cesarean delivery.

Although “music” is an all-encompassing term that describes sound with different pitches and rhythms that comes together as a harmonious whole, not all music is the same. Using “music” for therapeutic purposes would be the equivalent of using “antibiotics” to cure an infection; it is too general of a term, and unlikely that such a general use of music would show a valid therapeutic benefit. However, Conrad et al. demonstrated that specific selections of Mozart piano sonatas, which have a specific rhythm and mode, improve patient anxiety through a biochemical mechanism (changing the plasma levels of IL-6 and epinephrine). Therefore, in this study, when we refer to “music,” we will specifically plan on using the same Mozart sonatas as described in Conrad’s prior studies.

2.2. Risks to Subjects

Participation in this study will include a risk that if the music is too loud, injury to the tympanic membrane may occur. This complication will be avoided with the patient’s active participation at all times to report if the music is too loud, and volume will be adjusted according to the patient’s preference.

Psychosocial (non-medical) risks include the concern for coercion to participate. To minimize this risk, the co-investigator of the study, who is an anesthesia research fellow, will recruit all participants greater than or equal to one hour prior to participation in the study.

Other risks may include the unintentional loss of patient confidentiality. In order to minimize that risk, all paperwork will be stored in a secure location. Furthermore, all electronic data will be held in a Tufts Medical Center provided, password protected, encrypted, Box storage account.

2.3. Potential Benefits to Subjects

There is no direct benefit for participation in the study.

Subjects being randomized to the intervention arm, Mozart music, may receive greater overall satisfaction with their delivery experience.

2.4. Alternatives

The alternative is not participating in the study.

3. Objectives

The objective of this study is to determine the effect of music on patient satisfaction and anxiety during cesarean delivery. We will evaluate this objective by studying the following outcomes:

- The primary outcome of this study is patient satisfaction. This outcome will be measured using Morgan's "Maternal Satisfaction Scale for Cesarean Section" (MSSCS) on post-operative day one during the hours of 8am-1pm.
- The secondary outcome will include anxiety at several time points (immediately prior to and after neuraxial technique placement as well as at the end of surgery). This will be evaluated using a simple numeric rating score from 0-10, where 0 is no anxiety and 10 is the greatest anxiety.

We hypothesize that parturients exposed to music during cesarean delivery will have greater overall satisfaction and less anxiety.

4. Enrollment and Withdrawal

4.1. Inclusion Criteria

- Age: 18-50 years old
- Scheduled for elective cesarean delivery
- Nulliparity
- Singleton pregnancy
- Planning cesarean delivery
- Full term fetus (≥ 37.0 weeks gestational age)
- Healthy fetus (no known congenital diseases at the time of surgery)
- Requesting neuraxial anesthesia for the procedure
- Able to provide informed consent
- Spontaneous labor

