4.4. Recruitment and Retention

4.4.1. Local Recruitment Methods

Faculty in the Obstetrics and Gynecology Department at Tufts Medical Center will be informed about the study at one of the departmental meetings. They will be asked to inform their patients about this study in their clinic visits. The co-investigator, [name] will review medical records and schedule of medical procedures to know their time and date. Once the patients arrive to the labor and delivery unit, he will meet with the patients and discuss the study with them further. If they agree to participate, informed consent will be obtained.

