5.1. Study Timelines

- Participation begins at the time of consultation for cesarean delivery on the day of surgery, where the co-investigator [name] will approach the participants and ask them to sign the ICF, and it ends after the post-anesthesia check on postoperative day 1. After recruitment and consent, patients will be randomized using a computer-generated randomization scheme will be used to allocate patients to one of the arms of the study.
- The two arms of the study are as follows:
 - Control group: baseline hemodynamics and anxiety screen; no music
 - Intervention group – Mozart: A study investigator will turn on a playlist of pre-selected Mozart music.
- Given our sample size calculation and that not all women who are approached will consent to the study, we expect recruitment to take 12 months.
- The estimated date for primary analyses will be November 2018
- We estimate that it will take an additional 12 months to complete the study, including statistical analysis and manuscript preparation.

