5.2. Procedures

- Is there a placebo control arm?

Yes No

After reviewing their medical records, the co-investigator, [name], will approach parturients meeting inclusion criteria on the day of admission for scheduled cesarean delivery at Tufts Medical Center. The

PROTOCOL TITLE: A Randomized Controlled Trial of Music vs. No Music During Cesarean Delivery on Patient Satisfaction

VERSION DATE: Oct 16, 2017

research study will be explained and parturients will be given an informed consent form to read. After the parturient read through the informed consent form, think about the risks and benefits, and ask questions, she will be asked to sign the form if she wishes to participate in the study. The informed consent form will then be stored in the principal investigator's locked office. Once a study subject is enrolled, the anesthesia provider, obstetric provider, as well as the nurse will be informed that this parturient is part of the study.

Once the subject is recruited, patient demographic data and baseline vitals signs (including anxiety levels) will be collected. All parturients will receive a standardized spinal technique using 1.6 mL of 0.75% hyperbaric bupivacaine with 15mcg fentanyl and 200mcg morphine, which is the typical standard dose at Tufts Medical Center in nulliparous parturients.

Upon entry into the operating room, parturients who are randomized to music will start to listen to the Mozart piano sonatas during the entire procedure, while those randomized to no music will not listen to any music. After at least 5 minutes of listening to music and immediately after the spinal anesthetic is placed, anxiety levels and vitals signs will be assessed again. At the end of surgery, after coming into the PACU, anxiety and vitals will be assessed. Finally, on postoperative day 1, during the hours of 8AM – 1PM, patient satisfaction will be assessed by administering the MSSCS, which should take about 10 minutes to complete. After that, her participation in the study will end.

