6.1. Informed Consent Process

Will subjects be required to provide informed consent?

Yes No

- The parturients will be informed about the study during a clinic visit before being admitted for surgery.
- The informed consent will be taken in a private room in the labor and delivery unit on the day of the procedure.
- The patient will have one hour before the start of the procedure to make a decision regarding enrollment.
- The consent will be obtained in person and documented in writing following “SOP: Informed Consent Process for Research (HRP-090)”.
- Non-English speakers will be enrolled using interpreters and IRB approved Short Forms per the IRB's Short Form policy

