8.3. Number of Subjects

- A previous study demonstrated that the total satisfaction score in parturients who get midazolam pre-operatively vs. those who do not is 130.3 ± 10.5 vs. 113.6 ± 11.9 , respectively. Although we do not have similar data for music, we expect that the effect of Mozart music will be similar to that of midazolam because both music and midazolam work as anxiolytics and may play an important role in patient satisfaction. Therefore, we will expect to see a similar difference in patient satisfaction.
- Using G*Power 3.1, we determined that in order to detect a difference between the two groups using a two-tailed T-test with power of 80% and alpha of 0.05, the total number of subjects needed is 18. In order to account for 20% attrition rate, the total number of subjects that would be required to complete study aims is **22**.

VERSION DATE: Oct 16, 2017

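### As written, the eligibility lists exclude a woman scheduled for elective cesarean who is not in labor, and the labor terms are undefined

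*Combined protocol and SAP*

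**What the plan says.** Section 4.1 has 10 inclusion bullets. One is "Scheduled for elective cesarean delivery" and the last is "Spontaneous labor". They stand as separate items, with no word to make them alternatives and no qualifier. Section 4.2 has 11 exclusion bullets, one of which is active labor. Each labor term appears once in the available text, without a definition.

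The recruitment sections describe women coming to a planned operation:

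- Section 4.4.1: the co-investigator "will review medical records and schedule of medical procedures to know their time and date".
- Section 5.1: "Participation begins at the time of consultation for cesarean delivery on the day of surgery".
- Section 5.2: the co-investigator "will approach parturients meeting inclusion criteria on the day of admission for scheduled cesarean delivery at Tufts Medical Center".
- Section 6.1: "The parturients will be informed about the study during a clinic visit before being admitted for surgery", and "The informed consent will be taken in a private room in the labor and delivery unit on the day of the procedure".

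Section 10.2 makes the co-investigator responsible for confirming eligibility and taking consent ahead of any trial procedure.

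**The concern.** A list of inclusion criteria applies cumulatively unless it says otherwise, and Section 5.2 applies this one as a whole. One bullet calls for an elective operation booked in advance; another calls for labor that has begun on its own. The trial finds its women from a booking schedule, so one would expect many of them not to be in labor, yet the list turns those women away.

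Two things are at stake. The first is enrolment: whoever screens must either enforce the bullet and lose scheduled women not in labor, or pass over it and enrol women who do not meet the written criteria. The second is interpretation: a reader of the results could not tell whether the women were in labor, and so to whom the findings on satisfaction and anxiety apply. The planned data would not clearly settle this afterwards. Section 5.2 names demographics, vital signs and anxiety, and Section 8.4 names identifiers, vital signs and service dates; neither names labor status.

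**Working it through.** This is a check of logic, with only a little arithmetic.

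**Step 1. The rule as written.** From Sections 4.1 and 4.2:

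eligible = scheduled elective cesarean AND spontaneous labor AND NOT active labor (AND the remaining criteria).

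**Step 2. Apply it to a scheduled woman who meets every other criterion.**

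| Labor status | Labor bullet in 4.1 | Labor bullet in 4.2 | Eligible as written |
|---|---|---|---|
| Not in labor | Not met | Not excluded | No |
| Spontaneous labor, not yet active | Met | Not excluded | Yes |
| Spontaneous labor, active | Met | Excluded | No |

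The lists do not contradict each other outright, since the middle row survives. But they admit that row alone, and its boundary with the third row rests on two undefined terms. Two screeners could classify the same woman differently.

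**Step 3. Look for a passage that resolves it.** Sections 4.4.1, 5.1, 5.2 and 6.1 cover recruitment and consent. None of the four states a labor requirement. The word labor occurs in 4.4.1 and 6.1 only in the name of the unit, and not at all in 5.1 or 5.2. Section 5.2 does not override the bullet: by referring to women who meet the inclusion criteria, it carries the bullet along. No available section waives or explains it. The schema under Section 1 is not reproduced in the text reviewed, and the text between Sections 10.2 and 10.4 was not available.

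**Step 4. Size.** Let p be the share of enrolled women who are in spontaneous, not yet active labor. If the bullet is not enforced but the active-labor exclusion is, the number of deviations from this bullet is 22 × (1 − p), using the planned total of 22 from Section 8.3. The documents do not give p. At p = 1 the count is 22 × 0 = 0; at p = 0 it is 22 × 1 = 22. If the bullet is enforced, the loss to recruitment also depends on the unit's volume, which is not given either.

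**Step 5. What is not affected.** The calculation in Section 8.3 uses two means with their standard deviations, alpha, power and attrition: 18 × 1.2 = 21.6, rounded up to 22. Labor status is not an input. Section 5.1 places randomization after consent, so a misreading of eligibility would act before allocation and would not by itself favor an arm.

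**The case against.** The best reply is that this is drafting residue of little consequence. The criteria can be satisfied together by a scheduled woman in early labor. The recruitment sections describe logistics, and 4.4.1, 5.1 and 6.1 do not repeat age, parity or gestation either, so their silence on labor proves no conflict. Other signs point to leftover text: Section 4.1 carries a second, redundant bullet on planning a cesarean, and Section 8.5 mentions three arms in a trial with two. The rest of the population is clear enough: nulliparous women having a scheduled cesarean under a standardized spinal. A range of 0 to 22 out of 22 is the whole possible range and says nothing about the likely harm.

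Much of this stands. The lists are not mutually exclusive, the silence of the recruitment sections is weak evidence taken alone, only labor status is unclear, and the size is unknown. None of it cures the text. That the bullet is a leftover is an inference the protocol does not state, and a screener bound by Section 10.2 cannot drop a written criterion on that ground. If the early-labor group is in fact intended, nothing in the available text says so, and the boundary that defines it is missing.

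**Conclusion.** The point holds. The written rule makes a scheduled woman who is not in labor ineligible, it rests on two undefined labor terms, and no available section resolves it. It should be fixed because following the rule misdirects enrolment and ignoring it creates eligibility deviations. The effect falls on who may enter, on deviation reporting and on generalizability, and not on the sample size or the randomized comparison. Its size is bounded only by 0 and 22 of 22 women.

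The conclusion assumes that the inclusion bullets are cumulative, as Section 5.2 implies, and that neither the schema nor the other unavailable text holds a definition or waiver. That schedule-based recruitment would bring in many women not in labor is an expectation, not a figure from the documents.

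**What to change.** Reconcile Sections 4.1, 4.2 and 5.2 by a one-line amendment so that they state one labor-status rule consistent with the scheduled-cesarean population, and define any labor term that is kept. Deleting the bullet "Spontaneous labor" is the simplest wording that sits with Sections 4.4.1, 5.1, 5.2 and 6.1, but the sponsor must say which population is intended. Bring any eligibility checklist into line, and record labor status at consent so that the enrolled population can be described.

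This is best done before the first woman is enrolled. The documents do not say whether enrolment has begun; if it has, note the labor status of women already entered and report those who did not meet the criteria then in force. The cost is the amendment, its IRB review under Section 10.4, a checklist edit and one data field.

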4.2. Exclusion Criteria

- Patient refusal
- Prior history of extensive abdominal surgery
- Active labor
- Contraindication to neuraxial anesthesia
- Uncorrected coagulopathy
- Infection at the skin site of epidural placement
- Increased intracranial pressure
- Untreated hemodynamic instability
- Known hypersensitivity to local anesthetics (a.k.a. amide or ester allergy)
- Patients with impaired hearing
- Patient on anti-anxiolytic medication

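### The medication exclusion in 4.2 is worded in reverse, probably by a slip, so read literally it does not keep out women taking anxiolytics

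*Combined protocol and SAP*

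**What the plan says.** The last exclusion criterion in 4.2 reads "Patient on anti-anxiolytic medication". It has no drug list, dose or time window, and it is the only criterion in 4.1 or 4.2 about medication that a woman is taking. The procedures in 5.2 do not restrict anxiolytics or sedatives either.

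Section 8.3 takes its effect size from an earlier comparison of the "total satisfaction score in parturients who get midazolam pre-operatively vs. those who do not", given as "130.3 ± 10.5 vs. 113.6 ± 11.9". It carries that difference over to music because "both music and midazolam work as anxiolytics and may play an important role in patient satisfaction", and concludes that "we will expect to see a similar difference in patient satisfaction". Anxiety, on a 0–10 rating, is also a secondary outcome (sections 3 and 8.1).

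**The concern.** An anxiolytic reduces anxiety, so an 'anti-anxiolytic' would be a drug that opposes one. Taken at its word, the criterion excludes almost nobody, and a woman on an anxiolytic passes it. Yet these are the drugs that, on the reasoning in 8.3, share music's mechanism, and this line is the only entry safeguard against the overlap.

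Two things could follow if users were enrolled. If music adds the same amount for everyone, users and non-users sit at different satisfaction levels within each arm and the variance rises. If music adds little for women already on an anxiolytic, the average difference between arms shrinks. These are alternative scenarios, and their full effects should not be added together. Either would cost power for satisfaction, and the same argument applies to anxiety.

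**Working it through.** **Inputs.** From 8.3: means 130.3 and 113.6, SDs 10.5 and 11.9, a "two-tailed T-test with power of 80% and alpha of 0.05", and "the total number of subjects needed is 18". Allocation is assumed 1:1 (5.1 lists two arms and no ratio), so 9 per arm. The share of users, q, is not in the documents; 2%, 5%, 10% and 20% are assumptions.

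**The plan's own figure.**
- Difference = 130.3 − 113.6 = 16.7.
- Pooled variance = (10.5² + 11.9²)/2 = 125.93, so SD = 11.22.
- d = 16.7/11.22 = 1.488.
- Exact noncentral-t power, two-sided 0.05: 79.0% at 8 per arm and 84.2% at 9 per arm. The total of 18 is reproduced.

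**Scenario A: music adds 16.7 for everyone, and each user also carries 16.7.** The difference stays at 16.7. The SD in both arms is √(125.93 + q(1−q)·16.7²).

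**Scenario B: users gain nothing further from music.** The difference is 16.7(1−q). In the music arm users and non-users have the same mean, so the extra variance is in the control arm only. The average SD is √(125.93 + q(1−q)·16.7²/2).

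| Users q | A: SD | A: power | B: difference | B: SD | B: power |
|---|---|---|---|---|---|
| 0 | 11.22 | 84.2% | 16.7 | 11.22 | 84.2% |
| 2% | 11.46 | 82.7% | 16.4 | 11.34 | 81.9% |
| 5% | 11.80 | 80.5% | 15.9 | 11.51 | 78.4% |
| 10% | 12.29 | 77.2% | 15.0 | 11.77 | 72.0% |
| 20% | 13.06 | 72.1% | 13.4 | 12.18 | 59.0% |

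Example, q = 10%: q(1−q)·16.7² = 0.09 × 278.89 = 25.1. In A, SD = √(125.93 + 25.1) = 12.29 and d = 16.7/12.29 = 1.36. In B, the difference is 16.7 × 0.9 = 15.0, SD = √(125.93 + 12.55) = 11.77 and d = 1.28.

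**If the drug's gain is half as large (8.35 points).** With additive effects, SD = √(125.93 + q(1−q)·8.35²) and power is 82.4% at 10% users, 81.1% at 20% and 80.1% at 30%, so the 80% target is still met. That result depends on the effects adding. If a user's combined gain from drug and music is instead capped at 16.7, the difference is 16.7 − 8.35q and power is 79.4% at 10% and 74.2% at 20%, still well above the 72.0% and 59.0% of scenario B.

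**Chance imbalance.** One extra user in one arm of 9 moves that arm's mean by 16.7/9 = 1.9 points. The inflated SD above already includes this, so it is not a further loss.

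**The case against.** The strongest objection is that nobody would apply the line literally. The person who recruits and checks eligibility is an anesthesia research fellow (2.2, 10.2), working under a protocol that itself calls midazolam an anxiolytic. That reader would very probably take the intended meaning. This stands, and it limits the point to a defect in an operative eligibility rule. A reader might infer that the trial will in fact enrol women on anxiolytics; the documents do not show that.

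A reader might also infer that the protocol credits a 16.7-point gain to anxiolytics as a class. It does not. The figure is for pre-operative midazolam in one earlier study, and 8.3 says only that the shared mechanism may matter for satisfaction. Giving the full gain to every drug a woman might take is an extrapolation.

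Nor do the documents support a claim of bias between the arms. Allocation is randomized with concealed envelopes (8.5), so users would be spread by chance, leaving noise and possible dilution.

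Finally, the power figures follow the t-test of 8.3, whereas 8.2 names a chi-squared test for satisfaction. They therefore show scale on the plan's sample-size basis and are not the power of the analysis in 8.2. None of these objections makes the written criterion correct.

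**Conclusion.** The wording error is certain; its consequence is hypothetical. As written, 4.2 does not exclude women taking anxiolytics, and nothing else in the eligibility criteria or procedures does. If staff apply the intended meaning, nothing is lost. If they apply the text, the loss is negligible at 2% users (power 82–83% against 84%), marginal at 5% (78–80%), and material at 10% (72–77%) or 20% (59–72%).

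Those figures rest on 9 evaluable women per arm, 1:1 allocation, all such women being admitted, and each carrying the full 16.7 points. The shares are assumed, and a smaller gain gives a smaller loss. The sample size of 18 is unaffected, because the correction changes none of its inputs.

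**What to change.** In 4.2, replace 'anti-anxiolytic' with 'anxiolytic', so that the criterion agrees with the rationale in 8.3. Apply it at the medical-record review before approach (4.4.1, 5.2) and at the eligibility check (10.2). Which drugs and what look-back period it covers is for the sponsor to set. In doing so, the sponsor should note that the record review comes before consent and randomization, so it cannot show a drug taken between those steps.

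The cost is one line in an amendment, with no change to the sample size. A few women may become ineligible, as the criterion presumably intended.
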